#### 4.5.4 Dose Assignment and Adjustment

The following parameters will be summarized using descriptive statistics or frequency counts and percentages:

- Initial dose assignment (IU/kg)

- Final dose assignment (or assigned dose at datacut)
- Number and percentage of subjects ever assigned <20 IU/kg anytime during the study
- Number and percentage of subjects ever assigned >50 IU/kg anytime during the study
- Number and percentage of subjects with 0, 1, 2, >2 dose adjustments
- Number of dose adjustments
- Reason for dose adjustment.

The following prophylaxis regimens will be presented on dose assignment and adjustment tables:

- Every second day
- Three times per week
- Two times per week
- Other regimens

If a subject has two dose regimens on the same day, the frequency of the regimen will be summed and the doses will be averaged.

Dose assignment and adjustment for the main study will be summarized for the Safety and the Efficacy population.

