## List of Substantial Changes

The proposed revisions to the Version 1 of the Statistical Analysis Plan (SAP) dated 28 September 2016 and the rationale for these changes are summarised below.

SAP SECTION	REVISION	RATIONALE FOR REVISION
SAP Version 2 dated 10 September 2018		
General	REVISIONS MADE THROUGHOUT THE DOCUMENT: Protocol No. CSL627_3001 Amendment 2, 05 June 2015 REVISED TO Protocol No. CSL627_3001 Amendment 3, 27 January 2017.	To reflect the current protocol amendment.
Section 2.1 and 2.2 and accordingly throughout the document	Incidence of inhibitor formation to FVIII in Arm 2, PUPs was stated that would be performed on at least 50 PUPs. This condition has been removed.	Given that patients that develop inhibitors may be withdrawn from the study early, they would not necessarily achieve 50 exposure days. Therefore the text was adjusted to properly report the endpoint regardless of these circumstances.
Section 3.5.3	Efficacy Population definition has been changed removing the exclusive inclusion of subjects who do not have an inhibitor at any time point during the study.	Analysis by inhibitor status for PUPs will be included as a separate population and analysis.
Section 3.5.6	Region subgroups and Japanese subgroup added. Race subgroups added for inhibitors analysis.	To assess safety of CSL627 on regional and racial basis.
Section 3.5.6	Age subgroup changed to be based on age in this study.	To focus on age distribution in this study.
Section 4.1 and accordingly throughout the document	For PUPs, analyses of ABR, hemostatic efficacy, TEAE and IR will be presented overall and by inhibitor status.. Periods during which the subject receives injections for reasons different than prophylaxis are excluded.	To exclude periods in which other types of infusions might affect prophylaxis compliance.

Section 4.5.5	It has been specified that if a subject has two dose regimens on the same day, the frequency of the regimen will be summed and the doses will be averaged.	To handle mixed regimen assignment.
Section 4.5.7	Shift analysis in the current study from initial to final regimen has been added.	For completeness of analysis.

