#### 3.2.1 Prophylaxis Treatment Regimen

In previous studies, most subjects received prophylaxis treatment with an initial range of 15 to 50 IU/kg rVIII SingleChain every second day or 2 to 3 times per week.

- In Arm 1 and Arm 3 (PTPs), the investigator will determine the rVIII-SingleChain prophylaxis dose and dosing schedule for the subject based upon the subject's pharmacokinetic (PK) profile, rVIII-SingleChain PK data, previous FVIII treatment regimen, bleeding phenotype (if available), and taking into consideration the World Federation of Hemophilia (WFH) guidelines [[WFH, 2012](#)].
- In Arm 2 (PUPs), the investigator will determine the rVIII-SingleChain prophylaxis dose and dosing schedule at their discretion, taking into consideration the WFH guidelines [[WFH, 2012](#)], subject's age and other disease characteristics (e.g. bleeding phenotype).

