#### 4.5.3 Compliance and Adherence

Compliance will be summarized for the Efficacy population.

Compliance will be defined in terms of:

- The prophylaxis schedule, i.e. “prophylaxis compliance”. This is applicable only to the prophylaxis regimen.
- The prescribed dose, i.e., “dose compliance”. This is applicable to both the on-demand and prophylaxis regimens.

Prophylaxis compliance will be derived as:

$100 * (\text{number of on-schedule prophylaxis injections}) / (\text{expected number of prophylaxis injections})$ .

Expected number of prophylaxis injections will be computed considering the cumulative length of periods in which the subject has prophylaxis injections and the assigned regimen in these periods. Periods during which the subject receives injections for reasons different than prophylaxis are excluded.

Prophylaxis compliance will be categorized as 0 to < 80%,  $\geq 80$  to  $\leq 120\%$ ,  $\geq 120\%$ . Subjects whose prophylaxis compliance is not between 80% and 120% will be addressed in the periodic review of protocol deviations to determine whether they should be classified as non-compliant to the prophylaxis regimen.

Dose compliance will be derived as:

$100 * (\text{number of doses within } \pm 20\% \text{ of the prescribed dose}) / (\text{number of doses})$ .

Dose compliance will be summarized as a continuous and categorized as 0 to < 80%,  $\geq 80$  to  $\leq 100\%$ . Subjects whose dose compliance is not between 80% and 100% will be addressed in the periodic review protocol deviations to determine whether they should be classified as non-complaint to prescribed dose.

Adherence will be defined as having dose compliance and prophylaxis compliance (where applicable) based on medical review and assessment of protocol deviations.

CCI

Compliance will also be summarized while subjects are inhibitor positive on PUPs.

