#### 4.6.2.3 Consumption of rVIII-SingleChain

Consumption will be summarized as described in [Section 4.1](#). Consumption will be summarized for the Efficacy population and Safety population. The following parameters will be derived and summarized using frequency counts or descriptive statistics for subjects on the routine prophylaxis regimen:

- Total number of prophylaxis injections overall calculated as sum of all prophylaxis injections including all subjects;
- Prophylaxis dose administered per subject per month and per year (IU/kg):
  - per year calculated as: sum of prophylaxis doses (IU/kg) per subject\*365.25/(efficacy evaluation period);
  - per month calculated as: sum of prophylaxis doses (IU/kg) per subject\*(365.25/12)/(efficacy evaluation period);
- Total dose administered per subject per month and per year (IU/kg):
  - per year calculated as: sum of doses (IU/kg) per subject\*365.25/(efficacy evaluation period);
  - per month calculated as: sum of doses (IU/kg) per subject\*(365.25/12)/(efficacy evaluation period);
- Prophylaxis IU administered per subject per month and per year (IU):

- per year calculated as:  $\text{sum of prophylaxis doses (IU) per subject} \times 365.25 / (\text{efficacy evaluation period})$ ;
- per month calculated as:  $\text{sum of prophylaxis doses (IU) per subject} \times (365.25/12) / (\text{efficacy evaluation period})$ ;
- Total IU administered per subject per month and per year (IU):
  - per year calculated as:  $\text{sum of doses (IU) per subject} \times 365.25 / (\text{efficacy evaluation period})$ ;
  - per month calculated as:  $\text{sum of doses (IU) per subject} \times (365.25/12) / (\text{efficacy evaluation period})$ .

Each dose (IU/kg) will be calculated using the total international units (IU) recorded and the most recent recorded value of weight (kg).

The following prophylaxis regimens will be presented for consumption during routine prophylaxis:

- Three times per week
- Two times per week
- All frequencies.

Prophylaxis infusions are those recorded as administered for 'Routine/Prophylaxis'. Total infusions also include those recorded as administered for 'Bleeding Event', 'Surgery', 'Post Surgery', 'Prevention Prior to Activity', and 'Additional Treatment'.

The following parameters will be derived and summarized using frequency counts or descriptive statistics for subjects assigned to on-demand treatment:

- Number of infusions per subject per month and per year:

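### When two concurrent regimens differ in both frequency and dose, the SAP's rule of summing frequencies and averaging doses misstates the assigned dose

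*SAP*

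**What the plan says.** SAP 4.5.4 lists what will be summarized about prescribed dosing: initial and final assigned dose, the number of and reasons for adjustments, and two threshold counts, "Number and percentage of subjects ever assigned <20 IU/kg anytime during the study" and "Number and percentage of subjects ever assigned >50 IU/kg anytime during the study". It then names the prophylaxis regimen categories for these tables (every second day, three times per week, two times per week, other) and adds: "If a subject has two dose regimens on the same day, the frequency of the regimen will be summed and the doses will be averaged".

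The List of Substantial Changes gives the reason for this rule as "To handle mixed regimen assignment". The section states no weights for the average. It does not say whether the two threshold counts use the averaged dose or each dose as assigned.

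SAP 4.5.3 defines dose compliance as the share of doses within ±20% of the prescribed dose. It does not say which value is the prescribed dose for a subject on a mixed regimen.

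**The concern.** The rule builds one composite regimen from two. Adding the frequencies is right for regimens that run side by side. A simple mean of the doses gives each regimen the same weight however often it is given, so the composite frequency and the composite dose need not correspond to what the subject was assigned.

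Unequal frequencies are an ordinary case. Two whole-number weekly regimens can add up to the SAP's three-times-per-week category only as 2 + 1. Doses in this trial are set by the investigator, and these tables are how the SAP describes what was prescribed. At stake is their accuracy for subjects on mixed schedules, and whether the two threshold counts capture every subject who was assigned such a dose.

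**Working it through.** **Inputs.** The merging rule and the thresholds (20 and 50 IU/kg) come from SAP 4.5.4. The SAP gives no worked figure to reproduce and no actual mixed regimens, so the regimens below are assumptions. As orientation, SAP 3.2.1 says that in earlier studies "most subjects received prophylaxis treatment with an initial range of 15 to 50 IU/kg". The grid used here runs from 15 to 60 IU/kg so that it crosses both thresholds.

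**Formulas.** For regimens given f1 times per week at d1 and f2 times per week at d2:
- weekly dose assigned = f1·d1 + f2·d2
- weekly dose implied by the rule (simple mean) = (f1 + f2)·(d1 + d2)/2
- error = implied − assigned = −(f1 − f2)(d1 − d2)/2
- frequency-weighted mean dose = (f1·d1 + f2·d2)/(f1 + f2)

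The error is zero if f1 = f2 or if d1 = d2, and not otherwise.

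| Assumed regimens (times per week × IU/kg) | Merged by the rule | Implied per week | Assigned per week | Weighted mean dose | Error |
|---|---|---|---|---|---|
| 2×50 + 1×20 | 3×35 | 105 | 120 | 40 | −15 (−12.5%) |
| 2×30 + 1×60 | 3×45 | 135 | 120 | 40 | +15 (+12.5%) |
| 2×25 + 1×15 | 3×20 | 60 | 65 | 21.67 | −5 (−7.7%) |
| 1×30 + 1×60 | 2×45 | 90 | 90 | 45 | 0 |
| 2×40 + 1×40 | 3×40 | 120 | 120 | 40 | 0 |

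The first two rows have the same weekly total and the same mean dose per injection (40 IU/kg), yet the rule would table them as 35 and 45.

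**Grid.** Doses from 15 to 60 IU/kg in steps of 5 give 90 ordered pairs of unequal doses. With frequencies 1 + 1 the error is 0% in all 90. With 2 + 1 it is nonzero in all 90, from −16.7% to +25.0%. With 3 + 1 it is nonzero in all 90, from −23.1% to +42.9%.

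**Threshold counts, if they were built on the merged dose.** In row 2 a component of 60 is above 50, but neither the simple mean (45) nor the weighted mean (40) is. In row 3 a component of 15 is below 20, but the means are 20 and 21.67. Row 4 shows that this can happen even where the weekly dose is exact: 60 and 30 average to 45. On the grid with 2 + 1:
- of 34 pairs with a component above 50, 26 have a simple mean of 50 or less, and 24 a weighted mean of 50 or less;
- of 18 pairs with a component below 20, 16 have a simple mean of 20 or more, and 15 a weighted mean of 20 or more.

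Pairs with both doses beyond the limit stay visible (2×60 + 1×55 averages 57.5). These shares describe an assumed grid and are not expected patient frequencies.

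**Dose compliance, if the merged dose were the prescribed dose.** For 2×30 + 1×60 the simple mean of 45 gives a ±20% window of 36 to 54, and the weighted mean of 40 gives 32 to 48. Doses of 30 and 60 lie outside both, so a fully adherent subject would score 0%.

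**The case against.** The strongest reply is that this is one sentence about one descriptive table. The SAP never multiplies the summed frequency by the averaged dose, so the weekly totals above are constructions of this check. The word averaged does not exclude weighting. Actual dosing is reported independently: extent of exposure (SAP 4.5.2) takes dose per injection, and consumption (SAP 4.6.2.3) takes recorded units and weight. The table shells are in a separate document and may settle the programming.

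Much of this stands, and it limits the point. It does not remove it: the tabled dose per injection is also off (35 or 45 against 40), and with no weights stated the simple mean is the natural reading for a programmer.

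A reader might infer more than the documents support, in four ways:
- **That the merged dose is always wrong.** It is exact whenever the frequencies or the doses are equal.
- **That subjects are hidden from the threshold counts.** SAP 4.5.4 does not say that the averaged dose feeds them, and counting anyone ever assigned such a dose fits component records at least as well. Even with averaging, a subject is lost only if the mean falls back inside the limit.
- **That an old regimen ending and a new one starting on the same date would be summed,** for example 2 + 3 = 5 times per week. The logged purpose is mixed assignment, and nothing applies the rule to a change of regimen.
- **That the primary AsBR analysis is touched** through its prophylaxis-frequency subgroup (SAP 4.6.1.1). That subgroup uses frequency only, which dose averaging cannot change. For concurrent regimens the summed frequency is right, and the AsBR text does not refer to 4.5.4.

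**Conclusion.** The point holds as a correction to a derivation rule. With a simple mean, SAP 4.5.4 misstates the assigned dose whenever concurrent regimens differ in both frequency and dose. In the two main examples the error is 15 IU/kg/week, or 12.5% in either direction. Loss of subjects from the two threshold counts is a possibility that the SAP leaves open, not an established consequence.

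The reach is the descriptive dose-assignment tables, and dose compliance only if the averaged value is taken as the prescribed dose. Consumption, the inhibitor endpoints, hemostatic success and the overall AsBR do not use this value. The documents do not say how many subjects have mixed regimens, so the effect on the reported tables cannot be sized. The conclusion rests on reading averaged as unweighted and on assumed regimens. It concerns the derivation only and says nothing about which dose is appropriate.

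**What to change.** In SAP 4.5.4:
- Limit the rule explicitly to regimens that run concurrently. Keep the summed frequency, and report the frequency-weighted mean dose, (f1·d1 + f2·d2)/(f1 + f2).
- State that the below-20 and above-50 IU/kg counts are derived from each assigned dose record before any averaging. This must be said separately, because weighting does not restore those counts.

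One clause in SAP 4.5.3 should name the reference value for dose compliance under a mixed regimen. Neither mean works in the 30/60 example, so the dose assigned for the component regimen is the natural choice.

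The cost is two or three sentences and a small change to the derivation code. No new data are needed.

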#### 4.5.5 CCI

CCI

#### 4.5.6 Shift in modality and regimen

The shift in modality from the pivotal study to the current study will be described with shift tables, i.e. transition frequency tables, presenting number and percentages of subjects in each of the following categories:

- On-demand during the pivotal study and the current study
- Prophylaxis regimen during the pivotal study and the current study
- On-Demand during the pivotal study and Prophylaxis regimen during the current study
- Prophylaxis regimen during the pivotal study and On-Demand during the current study

The shift in modality from the pivotal study to the current study will be summarized for the Efficacy population for the PTPs Arm 1.

For prophylaxis regimen a table will be presented to summarize changes from initial to final regimen.

#### 4.5.7 Preventive and Additional Doses

Preventive doses of rVIII-SingleChain are allowed for subjects on on-demand and prophylaxis regimens. A preventive dose is defined as a dose that is taken prior to an activity or a minor procedure to prevent or minimize a bleeding episode.

Additional doses of rVIII-SingleChain are allowed for subjects on on-demand and prophylaxis regimens. An additional dose is defined as a dose that is taken within the 72 hours from the bleeding episode and beyond the need to control hemostasis and does not contribute to the efficacy evaluation of the bleeding episode.

These preventive and additional doses will not contribute to the efficacy evaluation of the bleeding episode and should be captured as “other treatments” in the subject’s eDiary if taken outside the hospital setting or eCRF (if administered in the hospital). Preventive and additional doses will contribute to EDs and consumption data.

The number and percentage of subjects with at least 1 preventive dose during the main study will be presented, and preventive doses will be summarized using descriptive statistics over the number of subjects with at least 1 preventive dose. In addition, the total number of preventive doses will be presented.

Similarly, the number and percentage of subjects with at least 1 additional dose will be presented, and additional doses will be summarized using descriptive statistics over the number of subjects with at least 1 additional dose. In addition, the total number of additional doses will be presented; and the total number of bleeding episodes requiring additional doses will be presented.

CCI

#### 4.5.8 Surgical Consumption

Summary statistics will be provided for the consumption of rVIII-SingleChain during surgery for the Surgery population. In particular summaries will be provided for the following time periods: pre-surgery, intra-operative, >0 to ≤72 hours, >0 to ≤168 hours, >0 to ≤336 hours and in total. Consumption for each surgery will be computed considering only doses within the corresponding surgery period. Moreover, individual consumption for each of the abovementioned time periods and in total will be listed. Results will be presented by Arm and age group. Consumption of rVIII-SingleChain on the calendar day of surgery will be also summarized for the following time periods: pre-surgery, intra-operative, post-surgery and total.

**Note:** If there are overlapping surgeries within 14 days, when calculating the consumption for the first surgery, we will censor this surgery at the beginning of the second surgery (indicated by pre-surgery dose, or surgery dose).

#### 4.5.9 CCI

CCI

CCI

#### 4.5.10 Concomitant Medication

Any medications taken concurrently with rVIII-SingleChain will be regarded as concomitant medications. Concomitant medication will be summarized for the Safety, Efficacy, Surgery and CCI populations.

For the Surgery population, only the medications that start during the surgical period will be reported.

CCI

The analysis datasets associated with concomitant medications will contain the flags defined below:

- **Prior:** the start date is either strictly prior to the reference date; or missing.
- **Concomitant:** either the start date or the end date is on or after the reference date; or the end date is missing.
- **Prior and concomitant:** both prior and concomitant.

Partial dates will be handled as outlined in [4.12.1](#). Concomitant medications will be coded using the World Health Organization (WHO) Drug dictionary version Q1, 2013. These will be summarized according to the Anatomical-Therapeutic-Chemical (ATC) classifications and preferred drug name.

Concomitant (i.e., prior and concomitant, or concomitant) medications will be summarized as defined in [Section 4.1](#). Only the number of subjects with concomitant medications (not the number of medications) will be presented.

Concomitant (i.e., prior and concomitant, or concomitant) medications will also be summarized while subjects are inhibitor positive on PUPs.

For concomitant medications which are linked to specific adverse events, the eCRF collects information to identify the specific adverse event. Concomitant medications used to treat COVID-19 associated adverse events will be summarized by ATC and preferred terms if the number of medications is at least equal to 10. Otherwise, concomitant medications used to treat COVID-19 associated adverse events will only be flagged in the listing of prior and concomitant medications.

## 4.6 Efficacy Analysis

The efficacy endpoints will be summarized and analyzed for the Efficacy population unless otherwise specified. The surgery substudy efficacy data will be summarized for the Surgery population. Efficacy analyses will be performed separately for the PTPs and PUPs and by modality. Efficacy results for the PUPs will be presented by inhibitor status (positive, negative) and overall.

The efficacy evaluation period begins on Treatment Day 1 date in this study and ends at the End of study Visit in this study or the last date of dose, whichever occurs later. Only those treated bleeding episodes and doses which fall within the efficacy evaluation period will count

towards the efficacy evaluation. The summary statistics to be presented are described in [Section 4.1](#).

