- A:** For subjects presenting with a bleeding episode at Screening, it is anticipated that Screening and Visit 1 may occur on the same calendar day, as the diagnosis of hemophilia A is likely to occur within the setting of an emergency.
- B:** Timing of visits as well as of distribution of rVIII-SingleChain for home treatment depends on timepoint at which the second bleeding episode occurs. Subjects will return to the site for a follow-up visit 1 month after each rVIII-SingleChain dose. However, multiple follow-up visits scheduled to occur within a 10-day time frame may be combined into a single visit (see example in Figure 4). For details, see Section 8.10.2.3.3.
- C:** Monthly phone calls only for subjects whose next bleeding episode does not occur within 1 month after the preceding visit.
- D:** One month is 28 days.
- E:** Inhibitor-negative PUPs will stay in this study until they have achieved 75 EDs; the overall study duration is expected to be up to 6 years. Additional time of up to 3 years in the study may occur for PUPs that develop an inhibitor: CCI [REDACTED]
- [REDACTED] ii) For inhibitor-positive PUPs who remain in the **main study** who have achieved eradication, the EOS visit will occur when they complete the 12-month post eradication follow-up period in the main study. The maximum duration of the inhibitor treatment period is 24 months starting when the dose is initially adjusted to treat the inhibitor, and if no dose adjustment is performed to treat the inhibitor then the duration of inhibitor treatment will be from the date of inhibitor diagnosis... In all cases, the EOS visit should take place at the end of the planned treatment period, if the subject discontinues prematurely, or if the sponsor terminates the study.
- F:** Unscheduled visits can be arranged at any time at discretion of investigator or upon request of subject or sponsor. The assessments performed at unscheduled visit are at discretion of investigator and are to be recorded in the eCRF.
- G:** If Screening and Visit 1 do not occur on the same calendar day, inclusion / exclusion criteria will be reviewed again to confirm subject eligibility.
- H:** If no medical record. Blood sample for gene defect should preferably be taken at Screening. If this is not possible, the sample can be taken at any time during the study.
- I:** Hematology: hemoglobin, hematocrit, red blood cell (erythrocyte) count, white blood cell (leukocyte) count, and platelet count.

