3.1 Study Design and Rationale

This multicenter, non-randomized, open-label, multiple-arm phase 3 extension study will continue to investigate the safety and efficacy of rVIII-SingleChain in PTPs with severe hemophilia A as well as in PUPs. This study will evaluate the prophylaxis and on-demand treatment of bleeding episodes in at least 200 PTPs who achieve at least 100 EDs as well as in PUPs who achieve at least 50 EDs. A surgical substudy (open to subjects from all study arms) will investigate the use of rVIII-SingleChain in surgery. CCI

[figure not shown]
Eligible subjects will be males who have been diagnosed with severe hemophilia A (FVIII activity levels < 1%). Subjects in Arms 1 are PTPs of any age who have participated in a previous CSL-sponsored clinical study with rVIII-SingleChain. Subjects in Arm 2 are PUPs

0 to < 18 years of age who have not participated in any clinical study with rVIII-SingleChain and have no other prior exposure to any FVIII product. Subjects in Arm 3 are PTPs 0 to < 65 years of age previously exposed to FVIII products (which may include rVIII-SingleChain) but who are not currently enrolled in a rVIII-SingleChain study.

Arm 2 PUPs can enter this study either at the time of their first bleeding episode or previously diagnosed with hemophilia A in a non-bleeding state.

This study is designed to collect data on the use of rVIII-SingleChain to assess long-term safety and efficacy beyond the outcome from pre-authorization clinical studies as well as to assess inhibitor development and characterize efficacy and safety of rVIII-SingleChain in PUPs. Inhibitor development is of particular interest for the safety of rVIII-SingleChain.

[figure not shown]
Figure 1: Study Overview of CSL627_3001

Abbreviations: ED = exposure day; PTP = previously treated patient; PUP = previously untreated patient.
A: Estimated duration of study participation to achieve the indicated number of EDs to rVIII-SingleChain.
B: All subjects who participate in Study CSL627_3001 are eligible for the surgery substudy at any time during the study.

CCI

Figure 2: Disposition Plan for PUPs

Abbreviations: CCI; PUP = previously untreated patient.

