8.10.2 Visit Schedule for Arm 2 (PUPs)

Summary of visit schedule for PUPs assigned to PROPHYLAXIS:

1. All PUPs assigned to prophylaxis receive their first rVIII-SingleChain dose in the clinic at Visit 1, either as a treatment dose for a bleeding episode, or as their first prophylactic dose under medical supervision.
2. At Visit 1, subjects will be provided with rVIII-SingleChain for prophylaxis therapy at home, if agreeable by the investigator.
3. After Visit 1, subjects will have monthly follow-up visits. Monthly visits continue until the subject reaches 25 EDs.
4. Once 25 EDs are reached, subjects will have 3-monthly follow-up visits until End of Study.

Summary of visit schedule for PUPs assigned to ON-DEMAND:

[figure not shown]
- All PUPs assigned to on-demand will receive their first rVIII-SingleChain dose in the clinic at Visit 1, either as a treatment dose for their first bleeding episode, or as their first exposure under medical supervision.
- Thereafter, the subject / caregiver can treat bleeding episodes with rVIII-SingleChain themselves, if agreeable by the investigator.
- Follow-up visits will occur 1 month after each rVIII-SingleChain dose. The following should be taken into consideration for scheduling these follow-up visits:
 - If the subject has a bleeding episode that spans multiple days or requires multiple doses, the follow-up visit should be scheduled based on the date of the last rVIII-SingleChain dose given for this bleeding episode.
 - If the subject has multiple rVIII-SingleChain doses within a 10-day timeframe, then the associated follow-up visits can be combined into a single visit if they occur ≤ 10 calendar days apart. In contrast, if the doses and the resulting follow-up visits occur at > 10 calendar days apart, separate follow-up visits must be performed (see example in [Figure 4](#)).
- If the interval between follow-up visits is > 1 month, monthly phone calls will be performed until the subject returns to the clinic for the next follow-up visit. These phone calls are mainly intended to collect information on bleeding status and AEs.

The timing of visits depends on the treatment assignment (ie, prophylaxis or on-demand) as well as on the clinical presentation at Screening for subjects assigned to an on-demand

regimen (ie, without or with a bleeding episode). This results in 3 different visit schedule options detailed in the following subsections and depicted in the algorithm in [Figure 3](#):

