#### **4.1.1 Data Handling Conventions**

##### **4.1.1.1 Reference Date and Study Day**

Timings of all safety events, interventions, and findings will be relative to the reference date. The reference date for this study will be the date of the first dose of rVIII-SingleChain defined as the date of first dose in this study.

Day 1 is the date of the Day 1 visit for this study (see CSP schedule of assessment for details).

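### The SAP has no rule for placing a bleed that began before the first dose, so a PUP's entry bleed can be counted in the primary bleeding rate

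*SAP*

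**What the plan says.** SAP 4.6 sets one window for all efficacy analyses: "The efficacy evaluation period begins on Treatment Day 1 date in this study". It closes at the End of Study Visit, or at the last dose if that is later. The section then adds: "Only those treated bleeding episodes and doses which fall within the efficacy evaluation period will count". SAP 4.1.1.1 makes the opening a calendar date and not a time: "Day 1 is the date of the Day 1 visit for this study". The Arm 2 schedules have no Day 1 visit, so I read this as Visit 1 for PUPs.

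Protocol 3.1 allows entry during a bleed: "Arm 2 PUPs can enter this study either at the time of their first bleeding episode". For those children, note A of the relevant Arm 2 schedules says "it is anticipated that Screening and Visit 1 may occur on the same calendar day". Protocol 8.10.2 describes the Visit 1 dose for PUPs assigned to on-demand as given "either as a treatment dose for their first bleeding episode, or as their first exposure under medical supervision", and for those assigned to prophylaxis as given "either as a treatment dose for a bleeding episode, or as their first prophylactic dose under medical supervision".

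SAP 4.6.1.1 limits the bleeding rates to bleeds that required treatment. Neither that section nor Protocol 11.3.2.1 removes a bleed that was present at Screening or began before the first dose.

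**The concern.** AsBR during prophylaxis and on-demand treatment is a primary endpoint of Arm 2, whose target is at least 24 PUPs. A bleed that was already under way when a child received his first dose says nothing about how well the product prevents bleeding. If it is counted, the rate rises by an amount that depends on how children came into the study and how long they were followed.

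The same bleed is legitimate evidence on a different question, namely how well rVIII-SingleChain stops a bleed. If it is major, it belongs to the other primary efficacy endpoint, treatment success. A single window serves both questions, so the way bleeds are placed in it affects both.

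The SAP separates pre-dose from post-dose findings elsewhere: baseline values (4.1.1.4), inhibitor results by date and time (4.7.1) and treatment-emergent adverse events (4.7.2). Bleeds have no equivalent rule.

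**Working it through.** The plan states no expected bleeding rate and no calculated sample size, so there is no figure to reproduce. The check has two parts.

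**1. Where the entry bleed falls.** The bleed is treated at Visit 1.

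| Entry bleed | Placed by treatment date | Placed by onset |
|---|---|---|
| Starts and is treated on Day 1 | Inside: counts in the rates and in hemostatic efficacy | Inside, because the window opens on the date: counts in both |
| Starts before Day 1, treated on Day 1 | Inside: counts in both | Outside: leaves both |

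The intended result is to leave the rates and stay in hemostatic efficacy. No cell gives it. A spontaneous entry bleed affects AsBR and the overall annualized bleeding rate (ABR); a traumatic one affects only the ABR.

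There is a further ambiguity in SAP 3.5.6, where the first inhibitor-negative period begins strictly after Time (start), a point the text does not tie to a date. If it is Day 1, a Day 1 bleed drops out of the by-status AsBR but stays in the overall AsBR.

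**2. Size.** The inputs are:
- Rate formula, bleeds / days × 365.25 (Protocol 11.3.2.1, SAP 4.6.1.1).
- Minimum of 8 weeks, or 56 days (SAP 4.6.1.1 and 4.11).
- 75 exposure days (EDs) for inhibitor-negative PUPs, and an expected study duration of up to 6 years (Protocol 3.3).
- Dosing every second day or 2 to 3 times weekly (Protocol 3.2.1). This describes previous studies and is used here only to turn EDs into days.

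One extra bleed adds 365.25 / days to a child's rate:

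| Follow-up | Days | Added bleeds per year |
|---|---|---|
| Minimum | 56 | 365.25/56 = 6.52 |
| 75 EDs, every second day | 75 × 2 = 150 | 2.44 |
| 75 EDs, 3 per week | 75/3 × 7 = 175 | 2.09 |
| 75 EDs, 2 per week | 75/2 × 7 = 262.5 | 1.39 |
| 1 year | 365.25 | 1.00 |
| 6 years | 2191.5 | 0.17 |

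For the pooled Poisson rate with N children, a share f entering with a spontaneous treated bleed that is counted, and mean follow-up of T years, the added rate is (N × f) / (N × T) = f / T. The documents do not give f, so the values below are assumptions:

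| f (assumed) | 150 days | 262.5 days | 1 year | 6 years |
|---|---|---|---|---|
| 0.25 | 0.61 | 0.35 | 0.25 | 0.04 |
| 1/3 | 0.81 | 0.46 | 0.33 | 0.06 |
| 0.50 | 1.22 | 0.70 | 0.50 | 0.08 |
| 0.75 | 1.83 | 1.04 | 0.75 | 0.13 |

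As an illustration, with f = 0.5, 262.5 days and a true rate of 2.0 per year (also assumed), the estimate would be 2.0 + 0.70 = 2.70, or 35% too high.

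**The case against.** A reader might infer that the plan states a rule counting pre-treatment bleeds. It does not. SAP 4.6 leaves the placing of a bleed open, and SAP 4.6.3.1 speaks of bleeds that occur during the evaluation period, which points toward onset. On that reading an entry bleed that began before Day 1 is outside the rate. The strict lower bound in SAP 3.5.6 may also keep a Day 1 bleed out of the by-status rates. Both arguments stand, and they limit the certain part of the problem to bleeds that start and are treated on the Day 1 date.

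A reader might also infer that the entry bleed is charged to prophylaxis when the child is then assigned to that regimen. No passage says so. Protocol 8.10.2 treats the dose for a bleed as an alternative to a first prophylactic dose, and Protocol 8.10.2.1.2 lists regimen assignment after that dose. Such attribution is possible, since nothing prevents it. It would shift the prophylaxis to on-demand rate ratio in SAP 4.6.1.1, in a direction that cannot be known in advance.

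The consequence is bounded. The protocol plans no p-values, and an added bleed works against the product. SAP 4.4 summarizes bleeding at Screening and SAP 4.6.2.1 lists bleed details, so entry bleeds can be traced. PUPs treated on demand gain EDs only as they are treated and may be followed for years, where the effect is small.

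None of this removes the gap: the date-based window, followed as written, puts a Day 1 entry bleed into the overall rate.

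**Conclusion.** The point holds as an unspecified attribution rule. It does not hold as a claim that the plan knowingly counts pre-treatment bleeds, or that it assigns them to prophylaxis. An entry bleed that starts and is treated on Day 1 counts in the overall AsBR if spontaneous, and otherwise in the ABR, whether bleeds are placed by onset or by treatment date. One with earlier onset either counts in the rate or is lost from hemostatic efficacy, depending on a choice the SAP has not made.

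The size ranges from minor to material. It depends on follow-up, on the share of PUPs who enter with a spontaneous bleed and on the true rate, none of which the documents give. It is largest with short follow-up on regular prophylaxis and nearly vanishes over six years. The conclusion also assumes that Treatment Day 1 means Visit 1 for PUPs. Because the endpoint is primary, the arm is small and the remedy is cheap, the rule should be written before the database is locked.

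**What to change.** In SAP 4.6 and 4.6.1.1:
- Place each bleed by its onset date and time.
- Exclude bleeds with onset before the first rVIII-SingleChain dose from the AsBR and ABR numerators: overall, by inhibitor status, by modality and in the rate ratio.
- Keep those bleeds in the hemostatic-efficacy analysis.
- When onset time is missing, treat a bleed that was present at Screening, or was treated by the first dose, as pre-dose.
- Report a sensitivity analysis that includes entry bleeds.

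In SAP 3.5.6, tie Time (start) to a defined date and time.

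The denominator needs no change, because PUPs receive the first dose at Visit 1. Protocol 8.3.2 already has the start of bleeding and the date and start time of each injection recorded in the eCRF, so no new data are needed. The cost is a few SAP sentences and a little extra programming.
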